## 9.6 Data Pooling

This study is, in part, being conducted to provide scientific evidence to support FDA clearance of the Elitone device. Accordingly, the FDA has provided input regarding aspects of the study design including the outcome measures and the sample size. As part of the regulatory review process, Elidah is considering augmenting data from this study with data from other studies. This approach may enable pooling of data from the multiple studies, which may reduce the number of required subjects in this study. If it is determined that fewer subject are necessary, Elidah may opt to terminate this study or alter the group assignment ratio. If this occurs, enrolled subjects will complete the full course of treatment.

## **10. DATA COLLECTION AND QUALITY ASSURANCE**

## **10.1 Data Collection Forms**

Subjects will provide data using the following forms:

- Pre-Study Questionnaire (TR-1131-FORM-1)
- I-QoL Questionnaire (TR-1131-FORM-2)
- Daily Log (TR-1131-FORM-3)
- Post-Study Questionnaire (TR-1131-FORM-3)

The forms are sent to the subjects in hardcopy and subjects return the completed forms to Elidah in envelopes with pre-paid postage. Returned forms are identified by the subject's ID Number and stored in the corresponding subject folder in the study binders. Electronic equivalents may also be utilized.

### **10.2 Materials Management**

In addition to the items described in 10.1, at the beginning of the study each subject will receive the following:

- Elitone controller and accessories (see 6.4)
- Elitone electrodes (see 6.3)
- User Manual (TR-1131-FORM-12)
- Absorbent pads
- Leak-proof specimen bags
- Pre-paid postage and packaging

Upon completion of the study, subjects in the active group are required to return the controller, accessories and any unused electrodes. Elidah will reconcile these components on the Case Report Form (TR-1131-FORM-10).

#### **10.3** Specimen Management

As part of the 24-hour pad weight tests, used absorbent pads will be mailed to Elidah to be weighed. Elidah will use universal precautions during receipt, inspection (i.e. weighing) and disposal of the specimens. Specimens will not be retained after they are weighed.

#### 10.4 Data Management

All subject folders and study binders will be kept in a locked cabinet at Elidah.

Data from the forms will be transferred to electronic formats (e.g. Excel) for analysis, but only in formats that do not include identifying subject data. This data may be generally accessible to Elidah staff and included in formal test reports within Elidah's Quality Management System.

Subject identifying data may be converted to an electronic format, but will not be generally accessible to Elidah staff.

In accordance with HIPPA requirements, at the conclusion of the study all study binders (or equivalent electronic files) will be maintained under lock and key for a minimum of seven years after last patient participation.

## 10.5 Data and Safety Monitoring Plan

Elidah will identify a Clinical Director who will be responsible for managing the study and ensuring that the rights and well-being of human subjects are protected, that the reported data are accurate and complete and verifiable from source documents, and that the conduct of the trial is in compliance with the approved protocol, with good clinical practice, and with applicable regulatory requirements. Specific responsibilities of the Clinical Director include:

- Verify that equipment and staff are adequate to safely and properly conduct the study
- Verify that subjects:
  - Meet eligibility requirements
  - Provided informed consent prior to enrollment
  - Are adequately informed about the device use, study requirements and risks of participation
  - Receive all necessary study materials
  - Return all the required data collection forms and specimens
- Verify that, with respect to the device:
  - That shelf-life and storage conditions meet requirements (as applicable)
  - Sufficient supplies (i.e. electrodes, controllers) are sufficient to complete the study
  - That the device is provided only to eligible subjects
  - That the receipt, use, and return of the device is controlled and complies with applicable regulation.
- Verify that source documents and data analyses are accurate and complete
- Verify that adverse events are appropriately reported
- Verify that protocol deviations are appropriately reported

In addition, a Data Safety and Monitoring Board will be established which will review study compliance and adverse events. The Data Safety and Monitoring Board will comprise, at a minimum, the Clinical Director, an individual responsible for technological aspects of the device and an individual with medical training relevant to the used of the device.

Currently, EMS and TENS devices are sold over the counter and used in an at-home environment. Given the high degree of similarity between those devices and the Elitone device, the described level of monitoring is considered appropriate for the low level of risk (see 7).

## 10.6 Quality Assurance

- **Training** –The Clinical Director is responsible for ensuring that the study staff can perform the responsibilities they have been assigned. All study staff will be required to complete the NIH Protection of Human Subjects Training before performing any function of the study.
- Quality Control Committee Given to the small scope of the study, a Quality Control Committee will not be utilized. The Clinical Director has responsibility pertaining to maintenance of study quality, and the Data Safety and Monitoring Board exists to ensure appropriate human protection regulations are met and adverse events are appropriately handled.
- Metrics Section 9.5 defines that data analysis and statistical approach used to determine study success. Upon completion of the analysis one or more persons not

involved with the original data analysis will audit the data entry, mathematical calculations and statistically driven conclusions.

• **Protocol Deviations** – Protocol deviations will be documented using Protocol Deviation Log (TR-1131-FORM-8) and retained within the Study Binders. The Clinical Director and/or Data Safety and Monitoring Board will make the determination of whether the impact of the deviation should be considered in subsequent analysis.

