#### 9.3 Blinding

Subjects will be blinded to their treatment group. As described in 6.6, with the exception of the firmware loaded on the Controller component, the devices used in the active and control groups are identical, so visualization and handling of the device by the subject will not compromise the blinding. The devices in both groups generate an electrical output that is perceived by the subject, which reduces the risk of subjects identifying themselves as in the control group. The device user manual (TR-1131-FORM-12) and subject instructions (TR-1131-FORM-15) have been modified/written to eliminate language that might suggest to a subject that she is one group or the other. Similarly, study personnel will be instructed to avoid use of language that might indicate which group a subject is enrolled.

Randomization as defined in 9.2 is implemented by an individual who does not interact with the subjects. Study staff who interact with the subjects are blinded to the randomization. Note however, that there is a risk that study staff who interact with the subjects may be informed of group assignment based on comments by the subjects during the study (e.g. if the subject

<sup>2 Richardson et al, "Pelvic floor electrical stimulation: A comparison of daily and every-other-day therapy for genuine stress incontinence", Adult Urology, 48(1):110-118, 1996.

describes the stimulation in a way that makes the stimulation identifiable). Such comments would be documented in the subject's Case Report File. This unblinding would have little impact on data integrity as the study personnel is not involved in the reporting of outcome measures.

Study personnel who analyze individual subject data will be blinded to group assignment. For example, baseline and 12th week episodes/day calculations and pad weight measurements will be made for each subject by blinded study personnel. Later, when group analysis is performed, blinding will be necessarily broken due to the unequal enrollment ratio.

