### 9.5 Data Analyses

Analysis of the **primary efficacy endpoint** will proceed as follows. Each adherent subject's Daily Log will be used to determine the average number of SUI episodes per day for the baseline and  $12^{th}$  weeks (see 5.5 regarding subject adherence). To accommodate the likelihood that some subjects will omit log data, the "weeks" referred to in the baseline and 12th week assessments refer to the first and last 5 entries in the Daily Log. The percent reduction in SUI episodes is then calculated by subtracting the final week average from the baseline average, dividing the difference by the baseline average, and multiplying by 100. Subjects with a percent reduction of  $\geq$ 50% are considered responders. The number of responders from each group is then compared using a one-tailed Fisher's exact test for groups of unequal size, and p $\leq$ 0.025. For example, if 24 of 40 subjects (60%) from the active group responded and 5 of 20 (25%) from the control group responded, the active treatment would be considered effective (p=0.01).

SUI episodes per day data can additionally be characterized simply in terms of percent reduction (independent of whether it reaches a 50% level of clinical significance) and the treatment groups analyzed using a 2 sample t-test with unequal group sizes. This approach is commonly reported in the literature. This value may additionally be reported but is not intended for use in determining whether the study met its endpoint. This use of a secondary analysis method on a single endpoint after success of the primary analysis method is generally understood to not inflate the Type 1 error rate, so no multiplicity adjustments are necessary.

Also note that confidence intervals and associated effect size calculations may also be made on the same data, but no multiplicity adjustments are warranted. Similarly, the data may be additionally analyzed using intent-to-treat criteria instead of with per-protocol criteria as defined in 5.5.

Regarding **secondary outcome measures**, three tests are prospectively defined with the intent of using the results to support future product labeling and marketing. The Hochberg procedure

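### The only independent audit of data entry is set for after the unblinded analysis; the entry check and a data lock should come before the arms are revealed

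*Combined protocol and SAP*

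**What the plan says.** Section 10.6 (Metrics) first refers to the 9.5 analysis as the one that decides study success. It then sets the time of the audit, "Upon completion of the analysis one or more persons not", and its scope: those people, not "involved with the original data analysis will audit the data entry, mathematical calculations and statistically driven conclusions". One audit, with one timing, therefore covers keyed data, arithmetic and conclusions.

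Section 9.3 sets the blinding sequence. Before the group analysis, "Study personnel who analyze individual subject data will be blinded to group assignment"; this includes each woman's baseline and week-12 episodes per day and her pad weights. After that, "Later, when group analysis is performed, blinding will be necessarily broken due to the unequal enrollment ratio". Section 5.7 says the same more briefly.

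Section 10.5 gives the Clinical Director a further duty: "Verify that source documents and data analyses are accurate and complete". It states neither when this is done nor whether the arm is hidden.

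Section 9.5 compares responder counts by a "one-tailed Fisher's exact test for groups of unequal size", with success at p of 0.025 or less. A responder has at least a 50% fall in mean daily stress episodes between the first five and last five log entries. Section 9.4 adds two interim looks, at 30 and 45 subjects, with the endpoint declared met if p is below 0.0013. Forms may be on paper or electronic (5.3, 10.1), and their data are transferred to electronic formats such as Excel (10.4).

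**The concern.** Blinded scoring protects the endpoint only while the scored data stay as they were when the arm was hidden. Under the stated order, the independent comparison of entered data with source starts after the arms and the p-value are available. Errors would be found, and decisions to correct them made, when it may already be clear which correction helps and which hurts. No misconduct need be supposed: an honest audit after a near miss may look harder for errors than one after a clear success, and that asymmetry is a bias. The same applies at the interim looks, where success can be declared with no audit stated beforehand.

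At stake is the primary efficacy conclusion of a 60-woman study that is meant in part to support a regulatory submission (6.7, 9.6). It rests on a dichotomy built from five diary entries at each end.

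**Working it through.** **Order of events, from the text**

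1. Subject-level figures are calculated with the arm hidden (9.3).
2. The group analysis is run and assignment is revealed (5.7, 9.3).
3. The independent audit of entry, calculations and conclusions follows (10.6).

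No section describes a lock, or an independent check of entered data, between steps 1 and 2. Section 9.4 mentions no audit before either interim look.

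**Inputs**

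- 40 active and 20 control (9.1).
- One-tailed Fisher's exact test, criterion p ≤ 0.025 (9.5).
- Worked example 24/40 v 5/20, stated p=0.01 (9.5).
- Responder rates: 60%/25% (9.1 and 9.5 example), 48%/13%, 62%/13% and 71%/15% (9.1 planning).
- Interim criterion p < 0.0013 (9.4).

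**The plan's own figure**

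With a active and c control responders and m = a + c, the one-tailed p is the sum over k ≥ a of C(40,k)·C(20,m−k)/C(60,m).

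For a=24, c=5, m=29, the terms for k = 24, 25, 26 and 27 are 0.00851, 0.00170, 0.00023 and 0.00002. Later terms are negligible. The sum is 0.0105, which agrees with the stated 0.01.

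**Reclassifying one woman at a time**

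| Active | Control | p | Against 0.025 |
|---|---|---|---|
| 24/40 | 5/20 | 0.0105 | success |
| 24/40 | 6/20 | 0.0269 | failure |
| 23/40 | 5/20 | 0.0167 | success |
| 22/40 | 5/20 | 0.0258 | failure |

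From the plan's example, one additional control responder turns success into failure. In the active arm it takes two lost responders.

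**How small an entry error suffices**

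Take, for illustration, a woman with 10 episodes over her five baseline entries. With 5 in her last five entries the reduction is (10−5)/10 = 50%, a responder. With 6 it is (10−6)/10 = 40%, a non-responder. One episode keyed wrongly changes her status.

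**How often a final result would be that close**

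For each pair of true rates, every (a, c) was weighted by its two binomial probabilities. The weights were summed over results where changing a or c by one crosses 0.025. The last column counts only failing results that are one change from success.

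| True rates | Within one reclassification | Of which failing, one short of success |
|---|---|---|
| 60%/25% | 30% | 14% |
| 48%/13% | 32% | 13% |
| 62%/13% | 9% | 3% |
| 71%/15% | 3% | 1% |

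**Interim look**

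Assuming the first 30 split 20/10, 15/20 v 1/10 gives p=0.0011 (endpoint met) and 14/20 v 1/10 gives p=0.0026 (continue). One status can decide an early declaration too.

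**The case against.** The strongest reply is that the plan already has safeguards. Each woman's episode averages and pad weights are produced by blinded staff before the group analysis, so her figures exist before the arms are known. The auditors are outside the original analysis. The Clinical Director must verify accuracy. Study binders are kept for at least seven years, so a correction can be tested against the woman's own record. Where electronic forms are used there may be little hand keying, and the documents give no error rate. All of this stands and lowers the risk. None of it fixes the scored data before the arms are revealed, and the Clinical Director's check has no stated timing or blinding and is made by the person who manages the study.

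A second reply is that tables beside a cutoff exist for any threshold test. That is fair, and it is why the closeness probabilities matter more than any single table. They are conditional on the true rates, and an entry error that crosses 50% in a pivotal woman must also occur.

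Four stronger readings might be inferred, and the documents do not support them:

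- That corrections will be made by people who know the arm and the result. The documents do not say who makes or approves corrections, and checking a log against source does not itself need the arm. It is a reasonable inference from one audit that also covers the conclusions, but it remains an inference.
- That the data are known to stay open after unblinding. The plan is silent on a lock; silence is not a statement that changes are allowed.
- That one woman decides the trial. This holds only when the result is near the boundary.
- That discarding pads after weighing (10.3) or staff access to de-identified data (10.4) adds to the problem. Pad weight is a secondary measure taken by blinded staff, and the access statement does not mention arm codes. Neither bears on the order of the audit.

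**Conclusion.** The point holds as a matter of sequence. The only independent audit of data entry that the plan describes follows the analysis that decides success, and by then the arms are known. No lock before unblinding is described, and no audit is stated before the interim looks. Existing safeguards make this a moderate weakness, not a fatal one; the change should be made.

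The size depends on the true responder rates. The chance that the final result is one reclassification from the boundary is about three in ten at 60%/25% or 48%/13%, and 9% or 3% at the two more optimistic planning pairs. These figures assume exactly 40 and 20 analysed women and independent binomial responses. They measure exposure to a single change of status, not the probability that an error or a biased correction occurs, which the documents do not allow one to estimate.

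**What to change.** Amend 10.6, with cross-references from 9.3 and 9.4, as follows:

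1. People not involved in the analysis check the entered data against source, and check each woman's episodes per day, percent reduction and responder status, with the arm hidden.
2. The dataset is then locked with a dated record, and arm codes are released only after that. This applies to the final analysis and to the data used at each 9.4 look.
3. The audit after the analysis keeps only the group calculations and the conclusions.
4. Any change after lock is logged with its reason, and the result is shown with and without it.

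Sample size, alpha and power are unchanged. The cost is small but not nil: the same check is done earlier, in instalments at the two interim looks and the end, with a short delay before each result and a change log to keep. The change does not settle how non-adherent women's data are adjudicated during analysis (5.5), which is a separate matter.

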#### **11. PARTICIPANT RIGHTS AND CONFIDENTIALITY**

#### 11.1 Institutional Review Board (IRB) Review

This protocol, including the informed consent document (see 11.2), and any subsequent modifications will be reviewed and approved by the IRB.

### 11.2 Informed Consent Form

TR-1131-FORM-5 includes information intended to allow the candidate to make the decision to provide informed consent, including descriptions of the protocol, participant requirements and potential risks. Among other requirements (see 4.1 and 4.2), individuals not allowed to participate in the study include:

- Minors
- Individuals who do not speak and read English
- Individuals who are unable to consent for themselves

Upon receiving the informed consent documentation the candidate may ask questions and take the necessary time required to read and comprehend the information. If the subject agrees to provide informed consent, she will sign an informed consent document. A copy is provided to the subject. Elidah's copy of the signed document is maintained in the Subject Folder. The consent may be an e-consent format.

#### **11.3** Participant Confidentiality

During the screening process (see 4.3) each candidate will be assigned a screening number. The subject's name and identifying data such as contact information will be stored in the Screening Log (TR-1131-FORM-11), which is maintained within the study binders (see 10.4).

One the subject is enrolled, her name is entered into the Enrollment Log (TR-1131-FORM-6). This is the only document that links the assigned Subject Number to a subject's name and contact information. The Enrollment Log is maintained within the study binders (10.4). All communication among study staff utilizes the Subject Number.

Identifying information will not be released without written permission of the subject except as required by the IRB, FDA or other regulatory body. In the event of written publication, results will be disclosed reflecting group statistics or without identifying information in order to protect subject confidentiality.

#### 11. APPENDICES

(As separate documents)

• TR-1131-FORM-1 – Pre-Study Questionnaire

- TR-1131-FORM-2 I-QoL Questionnaire
- TR-1131-FORM-3 Daily Log
- TR-1131-FORM-4 Post-Study Questionnaire
- TR-1131-FORM-5 Informed Consent Form
- TR-1131-FORM-6 Enrollment Log
- TR-1131-FORM-7 Subject Code Log
- TR-1131-FORM-8 Protocol Deviation Log
- TR-1131-FORM-9 Adverse Event Log
- TR-1131-FORM-10 Case Report File
- TR-1131-FORM-11 Screening Log
- TR-1131-FORM-12 User Manual
- TR-1131-FORM-13 Screening Questions
- TR-1131-FORM-14 Candidate Recruitment Language
- TR-1131-FORM-15 Subject Instructions

